## 2.9 Randomization of Trial Participants

For patients choosing not to be, or not able to be randomized, a baseline dropout form will ascertain the reason for dropout. Characteristics of randomized patients will be compared to those who are

excluded between the screening visit and randomization (either due to ineligibility or unwillingness to participate). In addition, the reason for nonparticipation will be recorded.

Consenting subjects will be randomly allocated in a 1:1 allocation to 6 times per week nocturnal home hemodialysis or three times per week conventional home hemodialysis. The randomization schedules will be prepared by the Data Coordinating Center (DCC) prior to the start of recruitment. Randomization will be stratified by Clinical Center and by diabetic status. Randomly permuted blocks of random sizes will be used to help balance numbers of participants assigned to both treatment regimens. This method guarantees that at no time during randomization will the participants in the individual groups be grossly unequal.

The randomization process will be centrally administered. All randomization schedules will remain confidential and known only by members of the Data Coordinating Center staff.

Once the patient has completed training for the generic portion of the home hemodialysis training process and all baseline studies have been completed and the forms corresponding to these studies have been received and checked to verify eligibility by the Data Coordinating Center,, the Principal Investigator or the study coordinator shall access the interactive randomization program. The program will verify through a defined set of questions that the participant is ready to be randomized and provide a randomized treatment assignment for that participant based upon his or her stratum. The randomization assignment will be displayed on the screen and emailed to the Clinical Center.

Randomization marks the participant's official and irrevocable entry into the Follow-up Period. Once a participant has been randomized, efforts will be made to conduct all evaluations irrespective of whether the patient starts the study treatment regimen, how long the patient continues on the study treatment regimen or not, and how well the patient complies to the study treatment regimen. These efforts should continue until termination of the Follow-up Period.

After randomization occurs, patients will begin training for the unique aspects of the assigned home hemodialysis modality. For patients assigned to nocturnal home hemodialysis, this will include training for the enuresis or leak detectors, access safety devices, addition of phosphate to the dialysate, etc). For patients assigned to the conventional home HD arm, this will include training in the handling of volume status and blood pressure, etc. It is anticipated that it will take one to two weeks to train an individual patient for these unique aspects of their assigned home hemodialysis modality. An individual patient will have no limit, however, on the time needed for training for these modality specific aspects of home hemodialysis.

## 3. Intervention Plan

## 3.1 Description of the Intervention: Dialysis Frequency and Dose

## 3.1.1 Summary of the Dose Intervention

Consenting patients meeting eligibility criteria will be randomized to 1 of 2 hemodialysis regimens, as shown in Table 4:

i) *Conventional home hemodialysis* of 3 sessions per week. Patients may remain on their usual dialysis prescription subject to a minimum delivered eKt/V of 1.1 per session AND a minimum treatment time of 2.5 hours per session;

ii) Long overnight home hemodialysis of 6 sessions per week, with a minimum treatment time of six hours AND a minimum delivered standard Kt/V (sKt/V) of 4.0

This design is intended to achieve a large separation in a wide range of treatment parameters related to small and middle molecule solute clearance, total weekly treatment time, and ultrafiltration, as shown in Tables 4 and 5.

## **3.1.2 Rationale for Choosing Target Doses**

## a) Conventional Home Hemodialysis Group

Hemodialysis dosing is based on clearance of urea, quantified as the Kt/V (K is the clearance of urea, t is time of dialysis session, and V is the volume of distribution of urea in the patient). Traditionally the single-pool Kt/V (spKt/V) has been used to define and measure dose in conventional hemodialysis. [Gotch, 1985] However, because the spKt/V overestimates true clearance due to the phenomenon of urea rebound, this trial will use equilibrated Kt/V (eKt/V). [Daugirdas, 1995; Pedrini, 1988]

The recently completed HEMO Study demonstrated that there was possible benefit of a higher dose of dialysis in women, but there was no recommendation to increase the dose of dialysis. [Eknoyan, 2002] The average dose of dialysis, as measured by the Daugirdas II equation in the CMS ESRD Clinical Performance Measures Project was  $1.46 \pm 0.27$  in 2000. [USRDS, 2001; USRDS, 2000; USRDS, 2002] This single pool Kt/V is equivalent to an equilibrated Kt/V of 1.25. In order to assure adherence to current national standards, a minimum delivered eKt/V of 1.10 will be required in the conventional home hemodialysis group. However, consistent with its designation as a conventional three times per week home hemodialysis arm, the dialysis prescriptions will be otherwise unspecified (subject to a minimum treatment time of 2.5 hrs).

Parameter	Conventional 3X/week HomeHD (control group)	Nocturnal Home HD (intervention group)	% Difference in medians; Nocturnal HD vs. Conventional HD
Sessions per week	3	6	+ 100%
Target delivered	minimum eKt/V of 1.1,	minimum sKt/V of 4.0	
Hours per session [median (mean = SD)]	$\geq 2.5$ (median = 3.50)	6.0 to 8.0 (median =7.0)	+ 100%
Maximum interdialytic interval during treatment week (median, hours)	68.5	41.0	- 40%
Average interdialytic interval during treatment week (median, hours)	52.5	21.0	- 60%
Hours per week (median, 5 th – 95 th percentile)	10.5 (9.0 – 13.1)	42.4 (36.6 – 47.6)	+ 304%

\* See Table 5 footnote for details of simulation.

Parameter	Conventional 3X/week Home HD (control group) (median, 5 th – 95 th percentile)	Nocturnal Home HD (intervention group) (median, 5 th – 95 th percentile)	% Difference in medians; Nocturnal HD vs. Conventional HD
eKt/V urea per treatment	1.39 (1.12 – 1.75)	1.56 (1.10 – 2.30)	+ 22.3%
Weekly sKt/V urea	2.46 (2.16 - 2.80)	5.60 (4.26 - 6.64)	+ 128%
Equivalent β2 microglobulin clearance (ml/min). Includes estimated extrarenal elimination rate of 3 ml/min	4.73 (4.12 – 5.32)	8.68 (7.66 – 9.99)	+ 84%
Estimated standard phosphate removal (mg/day). Assumes a pre-dialysis phosphorus level of 5 mg/dl	299 (254 - 374)	1191 (1028 - 1338)	+ 298%

 Table 5:
 Clearance of Selected Solutes\*

\* The median values and 5th and 95th percentiles given in Tables 4 and 5 were obtained from simulations with the following assumed distributions of treatment parameters based on a survey of the investigators from the Clinical Centers in the Nocturnal trial: Treatment time is distributed uniformly between 6 and 8 hours; dialysis blood flow is distributed uniformly from 300 to 500 ml/min for 50% of patients on single needle dialysis and uniformly from 200 to 300 ml/min for the other 50% assumed to be using double needle dialysis; dialysate flow is distributed uniformly from 200 to 300 ml/min, and urea KoA is 450 ml/min.

## b) Nocturnal Hemodialysis Group

Numerous conference calls with the nocturnal Clinical Center PIs have been held to discuss various aspects of the protocol. It was noted from these discussions that patients perceive less of a benefit from nocturnal dialysis when they dialyze for less than 30 - 35 hours per week. Based on this observation, the dose of dialysis will be prescribed by time and will include a minimum time of six hours six nights per week. The exception to this time prescription will be that the time will need to be increased if the measured standard Kt/V urea is less than 4.0. This exception is present to ensure an adequate separation between the standard and nocturnal groups in regard to urea kinetic modeling.

Simulation results indicate that the median sKt/V with 6 times per week nocturnal hemodialysis will be 5.12, with the 5th and 95th percentiles at 4.12 and 6.02, respectively. It is estimated that less than 5% of patients will have a sKt/V of < 4.0. To ensure that there is excellent separation between the conventional and experimental arms of the trial in regard to urea kinetics, a minimum delivered sKt/V for the nocturnal arm has been set at 4.0.

## 3.1.3 Calculation of Single Pool, Equilibrated and Standard Kt/V

Single pool Kt/V (sp Kt/V) will be calculated by applying the 2-BUN algorithm [Depner, 1989] to the predialysis and post-dialysis ureas collected according to current KDOQI (2006 dialysis update) [National Kidney Foundation', 2006] standards. The modification of the method of the Tattersall

rate equation will be used to estimate the equilibrated Kt/V (eKt/V) from spKt/V according to the formula:

 $eKt/V = spKt/V \times (T/(T + 30.7))$ 

where T denotes treatment time.

## 3.1.4 Data Collection, Determining the Initial Prescription and Monitoring Dose

Data to be obtained during the kinetic modeling sessions are summarized in Table 6. Although kinetic modeling data will be obtained monthly in order to fully characterize the interventions, the protocol for establishing and updating dialysis prescriptions is designed to minimize the number of prescription modifications and to be as unobtrusive as possible. The protocol for measurement of residual renal function is described in Section 3.1.5.

## a) Baseline Kinetic Modeling Session

Two kinetic modeling sessions will be conducted during the baseline evaluation phase of the trial.

In order to prevent randomization of prevalent patients who are unable to achieve a delivered eKt/V close of at least 1.10 in the three times per week home HD arm, patients must achieve an average delivered eKt/V of at least 1.0 for the two baseline kinetic modeling sessions in order to be randomized. If the average delivered eKt/V for the two baseline kinetic modeling sessions is less than 1.0, then an additional kinetic modeling session may be scheduled, and the mean delivered eKt/V recomputed from the last two baseline sessions. This process may be repeated up to 4 times, and the minimum eKt/V requirement will be met if at any of these tries the average eKt/V for the final two assessments exceeds 1.0.

## b) Determining and Monitoring the Trial Prescription during Follow-up

## i) Conventional Home Hemodialysis Group

Patients randomized to the three times per week conventional home HD group may follow any dialysis prescription provided their delivered eKt/V is at least 1.10 and treatment time is at least 2.5 hours. Modeling data will be obtained monthly, and prescribed eKt/V will be computed centrally based on the patient's current running median V over the preceding 4 months, and the patients current blood flow, dialysate flow, dialyzer type, single or double needle dialysis and ultrafiltration rate. (During the first months following randomization, the running medians will actually be obtained over 1-3 months, depending on the number of prior modeling sessions which have been conducted to that point in the trial.) If the delivered eKt/V falls below 1.10, using study ID numbers the Data Coordinating Center (DCC) will e-mail a warning to the study coordinator at the patient's Clinical Center, and provide alternative prescription options for a prescribed eKt/V of at least 1.10.

In addition, patients will provide a copy of their "run sheets" to the home hemodialysis training center on a weekly basis. Patients will not need to provide a copy of the run sheets if they are being monitored centrally. The information on the paper copy run sheets will include start and stop times, blood and dialysate flow rates and blood pressure and pulse readings. This information will be reviewed by the principal investigator for each Clinical Center and will be used to both determine if the patient is compliant with therapy and also for safety evaluations. Data from these run sheets will be provided to the DCC on a monthly basis.

#### Table 6: Data Collected at Kinetic Modeling Sessions\*

Treatment date
Start and end times (recorded)
Actual treatment time recorded on the dialysis machine, if available
Dialysate flow
Blood flow
Dialyzer type
Reuse number
Single or double needle dialysis
Interruption status (was total interruption time >30 min?)
Intradialytic hypotensive episodes and other symptoms requiring saline or reduced UF
Pre and Post HD systolic and diastolic blood pressure
Pre and Post HD weight
Pre and Post HD urea (local laboratory measurement)
Pre and post HD creatinine (local laboratory measurement)
Pre and post HD phosphate (local laboratory measurement)
Predialysis serum $\beta_2$ -microglobulin (to be measured in reposited serum specimens)

Predialysis serum albumin (local laboratory measurement)

## ii) Nocturnal Hemodialysis Group

After the first follow-up kinetic modeling session during the training period for nocturnal home dialysis, the Data Coordinating Center will determine if the minimum prescribed time on dialysis of six hours six times per week will achieve a target sKt/V of at least 4.0 If the minimum dose is insufficient, then the DCC will send an array of dialysis prescription options for a target sKt/V of 4.0. Subsequently, modeling data will be obtained monthly, and revised dialysis prescriptions will be provided if the running median V (over 4 months) increases by an amount that leads to a decrease in the updated prescribed sKt/V to a value less than 4.2. Failure to implement the revised prescriptions will be regarded as non-adherence to the protocol. This procedure is designed to minimize the chance that the running median achieved sKt/V would fall below the minimum delivered sKt/V of 4.0.

In addition, patients will provide a copy of their "run sheets" to the home hemodialysis training center on a weekly basis. Patients will not need to provide a copy of the run sheets if they are being monitored centrally. The information on the paper copy run sheets will include start and stop times, blood and dialysate flow rates and blood pressure and pulse readings. This information will be reviewed by the principal investigator for each Clinical Center and will be used to both determine if the patient is compliant with therapy and also for safety evaluations. Data from these run sheets will be provided to the DCC on a monthly basis.

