Patients assigned to the conventional three times per week home hemodialysis arm will follow any dialysis prescription subject to two constraints to assure compliance with minimum national standards: a) equilibrated Kt/V  $\geq$  1.1, b) treatment time  $\geq$  2.5 hours. Patients assigned to the 6 times per week nocturnal home hemodialysis arm will follow any dialysis prescription provided their prescribed standardized Kt/V is at least 4.2 and treatment time is at least 6.0 hours, 6 times per week. These prescriptions should provide large differences in median levels of key parameters between the nocturnal and conventional home three times per week hemodialysis groups including a standardized Kt/V of 5.21 versus 2.30; an equivalent renal clearance of  $\beta_2$ -microblogulin (relative to time-average concentration) of 9.03 versus 4.73 ml/min/35 L; a standardized phosphorus removal of 1281 versus 299 mg/day; a total weekly treatment time of 45.6 versus 10.50; and an ultrafiltration rate of 3.32 versus 13.48 ml/min.

Data to be obtained in the trial includes kinetic modeling visits held at baseline and monthly throughout the 12 month follow-up period including dialysis treatment and kinetic modeling parameters plus weight, blood pressure, protein catabolic rate, creatinine generation rate, monitoring of missed treatments over the previous month, serum albumin levels, local laboratory measurements and medication usage (including antihypertensives, erythropoietin dose, phosphate binders, IV iron dose, and vitamin D). Measures of quality of life, depression, physical function, and cost-effectiveness will be obtained at baseline and months 4 and 12. Bioelectric impedance will be performed at baseline and at months 4 and 12. Cardiac MRI will be obtained at baseline and month 12. Medical comorbidity assessment will be obtained at baseline... Vital status, hospitalizations, and access procedures will be monitored throughout follow-up. Potential risks of daily nocturnal home hemodialysis to be monitored include vascular access complications (evaluated by primary unassisted patency), iron losses, malnutrition, patient burn out and electrolyte abnormalities.

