## 2.2 Overview of Study Design

This will be a randomized, unblinded study of six times per week nocturnal home hemodialysis versus three times per week conventional home hemodialysis. A target of 90 patients will be enrolled into this study with equal allocation in each arm, stratified by Clinical Center and diabetic status. All patients will be assessed for suitability for nocturnal home hemodialysis using a standardized method prior to patients entering the baseline portion of this protocol. The minimum dialysis dose in the conventional home arm will be an equilibrated Kt/V of 1.1.In the nocturnal arm there will be a minimum prescription of six hours per session for six days per week AND a minimum achieved standard Kt/V of 4.0. Patients will be followed for 12 months.

Because no previous randomized trials of nocturnal dialysis have been conducted, the first calendar year after the initiation of enrollment has been designated as a "Vanguard" phase during which feasibility of randomization and conduct of the interventions will be evaluated. If pre-defined benchmarks for establishment of feasibility are achieved during the Vanguard phase, the trial will proceed to its primary objective of determining if 6 times per week nocturnal hemodialysis results in clinically significant improvements in physiological, health-related quality of life (HRQL) and functional outcomes, as compared with three times per week conventional home hemodialysis.

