## 7.2 Action Items

The DCC will report and the Outcome Committee will review (in conjunction with Kinetic Modeling Committee) any patient who has persistent underdialysis (i.e., for conventional home hemodialysis group, not meeting eKt/V of 1.10 per session for 2 or 3 consecutive measurements; for the nocturnal home hemodialysis group, not meeting a std Kt/V of 4.0 for 3 consecutive measurements)

- a) DCC will report and the Recruitment and Adherence Committee will review any patient who has persistent nonadherence to therapy. Persistent nonadherence to be defined and monitored with appropriate action by adherence committee (in conjunction with Kinetic Modeling Committee).
- b) DCC will report and the Standards of Care/Clinical Management Committee will review any patient who has persistent hypophosphatemia (serum phosphate level less than the lower limit of the normal range) on 2 or 3 consecutive monthly measurements
- c) The Central HRQL Survey Center will report within 24 hours to the research coordinator or treating nephrologist any patient who has potentially life-threatening findings on questionnaires done exclusively for the purpose of the study. These findings will also be reported to the DCC who will report these findings in a timely manner to the study center when received by the database. These findings may include, but are not limited to:
  - i) scores above a certain threshold that indicates depression on the Beck Depression Inventory
  - ii) answers 2 or 3 on question #9 of the Beck Depression Inventory ("would you kill yourself")
- d) The Central Cardiac MRI Core will simultaneously transmit a report to the Clinical Center, Data Coordinating Center and Consortium Core for any patient who has potentially clinically relevant findings on tests done exclusively for the purpose of the study. The DCC will report these findings in a timely manner (approximately 2-3 weeks from MRI Core Physician review) to the study center when received by the database. These findings usually include clinically relevant abnormalities noted during the performance of the cardiac MRI. These will relate to abnormalities noted in the pericardium, myocardium, valvular structures and/or contiguous vascular structures. Clinically relevant abnormalities will be adjudicated based on the best clinical judgment of the reviewing physician at the Central Cardiac MRI Core.

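### Section 3.1.4 b) ii) checks and builds the first nocturnal prescription at a target sKt/V of 4.0, the delivered minimum, although the prescribed floor elsewhere is 4.2

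*Protocol*

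**What the plan says.** The Executive Summary lets nocturnal patients follow any prescription "provided their prescribed standardized Kt/V is at least 4.2 and treatment time is at least 6.0 hours, 6 times per week". That is a floor on the prescribed dose.

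Section 2.2 sets "a minimum achieved standard Kt/V of 4.0". Sections 3.1.1 and 3.1.2 b) and Table 4 give the same 4.0 as a delivered minimum.

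Section 3.1.4 b) ii) then describes what the Data Coordinating Center (DCC) does:

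- After the first follow-up modeling session it checks whether the minimum time, six hours six times a week, reaches a target sKt/V of at least 4.0. If not, "then the DCC will send an array of dialysis prescription options for a target sKt/V of 4.0".
- In later months it issues a revised prescription if a rise in the running median V "leads to a decrease in the updated prescribed sKt/V to a value less than 4.2".
- The procedure is "designed to minimize the chance that the running median achieved sKt/V would fall below the minimum delivered sKt/V of 4.0".

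Two later safeguards exist. Section 3.1.2 b) says "the time will need to be increased if the measured standard Kt/V urea is less than 4.0". Section 7.2 sends for committee review a nocturnal patient "not meeting a std Kt/V of 4.0 for 3 consecutive measurements".

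**The concern.** A prescribed floor set above a delivered minimum gives delivery room to fall short of prescription without breaching the minimum. The monthly rule works this way. The initial step instead uses the delivered figure for both the check and the options, so the first prescription of a low-clearance patient depends on which section the DCC follows.

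The monthly rule does not clearly repair this. It is worded as a rise in V that brings the prescribed value down to below 4.2, which presupposes a start at or above 4.2. A patient who starts between 4.0 and 4.2 with a stable V is not plainly covered.

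At stake are the initial dose of some nocturnal patients and uniform practice at the DCC. Adherence records could also be touched, because Section 3.1.4 b) ii) counts failure to implement a revised prescription as non-adherence.

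**Working it through.** This is mainly a comparison of stated thresholds.

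**1. Thresholds side by side**

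| Place | Quantity | Value |
|---|---|---|
| Executive Summary | prescribed | at least 4.2 |
| 3.1.4 b) ii), monthly trigger | updated prescribed | below 4.2 |
| 3.1.4 b) ii), initial check and options | *target* | 4.0 |
| 2.2 | achieved | at least 4.0 |
| 3.1.1, 3.1.2 b), Table 4 | delivered | at least 4.0 |
| 7.2 | measured, 3 in a row | below 4.0 |

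Wherever the quantity is called prescribed, the value is 4.2. Only the initial step uses 4.0 to build a prescription.

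**2. The two readings of *target***

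- *Prescribed.* A first prescription from 4.0 up to, but not including, 4.2 satisfies the initial step and breaches the Executive Summary.
- *Delivered.* The thresholds do not contradict each other, but the sentence governs prescription options and names no prescribed value for them. The matching rule in the conventional arm does: the DCC will "provide alternative prescription options for a prescribed eKt/V of at least 1.10".

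**3. The margin**

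4.2 / 4.0 = 1.05, so the 4.2 rule gives a 5% margin over the delivered minimum. A prescription at 4.0 gives none.

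The documents give no within-patient variability, so the following is an illustration under assumptions: delivered values are normal around the prescription, and the median of four is taken.

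| Prescribed | Assumed CV | Chance that the median of four is below 4.0 |
|---|---|---|
| 4.0 | 3%, 5% or 10% | about 50% in each case |
| 4.2 | 3% | about 0.2% |
| 4.2 | 5% | about 4% |
| 4.2 | 10% | about 19% |

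**4. How many patients**

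Section 3.1.2 b) gives a simulated median of 5.12, with 5th and 95th percentiles of 4.12 and 6.02, and says that fewer than 5% fall below 4.0. That figure reproduces:

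- Lower-tail SD = (5.12 − 4.12)/1.645 = 0.608. P(sKt/V < 4.0) = Φ((4.0 − 5.12)/0.608) = 3.3%.
- With an SD averaged over both tails, 0.578, the result is 2.6%.

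For 4.2 no distributional assumption is needed. The 5th percentile is 4.12, and 4.12 < 4.2, so at least 5% of that simulated population lies below 4.2. For scale, 5% of the 45 patients in the nocturnal arm (90/2) is 0.05 × 45 = 2.25. Table 5 gives a higher 5th percentile, 4.26, so in that simulation no more than about 5% lie below 4.2.

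Neither figure counts the patients who would fail the initial check. The Table 5 footnote draws session time uniformly from 6 to 8 hours, whereas the check is made at 6 hours. Shares at 6 hours may be higher, but the documents do not allow them to be calculated.

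**The case against.** The strongest reply is that *target* is a delivered term in this protocol. Table 4 has a row for the target delivered dose, with a minimum sKt/V of 4.0, and the initial check asks what the minimum schedule will achieve. On that reading the Executive Summary supplies the prescribed floor, and only a cross-reference is missing. This is plausible and lowers the weight of the point. It does not remove it, because the sentence tells the DCC what to build prescriptions to and, followed literally, permits 4.0.

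A reader might infer that every patient whose six-hour schedule gives 4.0 to 4.2 is left with a prescription in that range. The documents do not support this. The check concerns the minimum time and does not cap the prescription; Table 4 shows 6.0 to 8.0 hours with a median of 7.0. Such a patient may well be prescribed longer and clear 4.2.

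It is also fair that the conventional arm has no margin: its delivered minimum and its prescribed value are both 1.10. But no higher prescribed floor is stated for that arm, so nothing there conflicts.

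Finally, the rule in Section 3.1.2 b) and the Section 7.2 review limit how long a low dose would last. Both stand as safeguards, but both act only once a shortfall has been measured.

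**Conclusion.** The point holds as a minor inconsistency in a decision threshold. The initial step in Section 3.1.4 b) ii) uses the delivered minimum where the Executive Summary and the same section's monthly rule use a prescribed value of 4.2. On one reading it conflicts with the Executive Summary; on the other it fails to apply the floor. Either way it sits badly with the section's stated aim of keeping achieved sKt/V at or above 4.0.

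Probably only a few nocturnal patients are affected. That rests on the protocol's simulated percentiles, which do not describe the six-hour check, so no count of patients who would or would not be sent options is justified.

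A reader might also infer that the efficacy comparison is compromised. It is not: Section 9.4 analyzes patients by randomized assignment irrespective of adherence, so the primary analysis, its Type I error control and the sample size are untouched.

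**What to change.** In Section 3.1.4 b) ii):

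- Check the patient's initial prescription (at least six hours, six times a week) against a prescribed sKt/V of at least 4.2.
- If it falls short, send options for a prescribed sKt/V of at least 4.2.
- Provide a revised prescription whenever the updated prescribed sKt/V is below 4.2, whether or not V has risen.

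Keep 4.0 as the delivered or achieved minimum in Sections 2.2, 3.1.1, 3.1.2 b) and 7.2 and in Table 4.

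The cost is a few sentences and one DCC threshold, plus slightly longer sessions or higher flows from the start for the patients concerned. If a prescribed 4.0 was really intended, the Executive Summary and the monthly trigger would have to change instead, and the margin over the delivered minimum would be lost. The 4.2 version fits the stated purpose better.
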